10.3 Potential Benefits.....	32
10.4 Risk-Benefit Rationale.....	32
11. Adverse Events and Device Deficiencies.....	32
11.1 Adverse Events.....	32
12. Statistical Design and Methods	33
12.1 General Aspects of Analysis.....	33
12.1.1 Sample Size.....	33
12.1.2 FlowMet-R data analysis and diagnostic model.....	33
12.1.3 Analysis of Stenosis	34
13. Ethics	34
13.1 Statement(s) of Compliance	34
14. Study Administration.....	35

14.1 Monitoring	35
14.2 Data Management.....	35
14.3 Direct Access to Source Data/Documents	35
14.4 Confidentiality	36
14.5 Liability	36
14.6 CIP Amendments.....	36
14.7 Record Retention.....	36
14.8 Suspension or Early Termination	37
14.8.1 Planned Study Closure	37
14.8.2 Early Termination or Suspension	37
15. References	37
16. Appendices.....	39
17. Version History.....	39

1. Glossary

Term	Definition
ABI	Ankle brachial index
AE	Adverse event
ATK	Above the knee
AUC	Area Under the (ROC) Curve
BTK	Below the knee
CCD	Charge coupled device
CDU	Color duplex ultrasound imaging
CI	Confidence interval
CLI	Critical limb ischemia
Cm	Centimeter
CMOS	Complementary Metal-oxide Semiconductor
CRF	Case report form
EDC	Electronic Data Capture
FDA	Food and drug administration
Hr	Hour
ICF	Informed consent form
IRB	Institutional review board
Nm	Nanometer
OHRP	Office of Human Research Protection
PAD	Peripheral artery disease
PPG	Photoplethysmography
ROC	Receiver operating characteristic

Term	Definition
SAE	Serious adverse event
TBI	Toe brachial index
US	United states

2. Synopsis

Title	FlowMet-R Blood Flow Measurement for the Diagnosis of Peripheral Artery Disease (PAD) and Critical Limb Ischemia (CLI)
Product Name	FlowMet-R
Sponsor	Medtronic Vascular, Inc. [name]
External Organizations	[REDACTED]
Investigation Purpose	The purpose of the investigation is to assess the efficacy of the FlowMet-R device in diagnosing PAD and CLI in patients scheduled for peripheral vascular examination. The results of the assessment of the FlowMet-R device will be compared to gold standard diagnostics including ABI, TBI, and Doppler Ultrasound.
Primary Objective(s) and/or Endpoint(s)	The primary objective is to determine the efficacy of FlowMet-R measurements in diagnosing PAD and CLI in patients during initial visit, three month, and six month follow-up.
Secondary Objective(s) and/or Endpoint(s)	The secondary objectives are to determine the capability of the FlowMet-R in prognosis of requiring vascular intervention or amputation within three and six months following the initial visit. Additionally, to investigate the correlation between FlowMet-R measurements and peripheral artery stenosis. Finally, to assess the correlation between changes in ABI/TBI/Rutherford Classification and changes in FlowMet-R data between any two time points.
Study Design	Multi-center, non-randomized, longitudinal study with three and six month follow-up.
Sample Size	PAD Cohort: Cohort will consist of 240 limbs with PAD including a minimum of 54 limbs with claudication and a minimum of 100 limbs with CLI. All comers - any patient scheduled for peripheral vascular

	
assessment who is not subject to exclusion may be approached for enrollment in the disease positive arm. Exclusion criteria are detailed in Section 8.4. This will include patients in the registry who have a planned endovascular or surgical intervention to address their PAD.
 
Healthy Cohort: Cohort will consist of 160 control limbs. Any patient over 40 years old and without suspected PAD may be approached for enrollment in the healthy control arm. Healthy subjects may be enrolled from other departments within the clinic/hospital, can be from the local community, or can be actively recruited for participation (such as researchmatch.com or active volunteers).
 
Registry: Patients diagnosed with PAD at baseline procedure who are scheduled to undergo an endovascular treatment of the lower limbs will be included in the registry data for this study. The registry will be established to record FlowMet-R measurements, angiographic films, and any additional relevant information immediately prior to, during, and immediately following peripheral vascular interventional procedures for enrolled patients.

Inclusion/Exclusion Criteria	
INCLUSION CRITERIA
 
PAD Positive Cohort:
 
– Subject meets PAD positive criteria set forth in Section 8.4– Subject is willing and able to provide informed consent– Subject is willing and able to comply with the study procedures– Subject is able to understand the study procedures– Subject is scheduled for vascular examination that includes noninvasive assessments as standard of care: ABI, TBI, and either a Duplex Ultrasound or Angiogram 
Healthy Cohort:
 
– Subject is willing and able to provide informed consent– Subject is willing and able to comply with the study procedures– Subject is able to understand the study procedures– Subject has no history of positive PAD diagnosis and is not currently suspected of having PAD 
EXCLUSION CRITERIA
 
PAD Positive Cohort:
 
– Subject is under 40 or unable to consent

	
– Subject has any medical condition, which, in the judgement of the Investigator and/or designee, makes the subject a poor candidate for the investigational study– Subject is excluded from analysis if no stenosis is found during Dopper Ultrasound, but Tibial disease is suspected and Tibial ultrasound is not able to be performed– Subject does not have a suitable finger to attach the FlowMet-R probe– Subject does not have a suitable 1st or 2nd digit to attach the FlowMet-R probe on the limb of interest– Subject has undergone revascularization within the last 90 days– Subject cannot lay safely in a supine position 
Healthy Cohort Exclusion:
 
– Subject is under 40 or unable to consent– Subject has any medical condition, which, in the judgment of the Investigator and/or designee, makes the subject a poor candidate for the investigational study– One or more of the limbs has a prior or current diagnosis of PAD, or is reasonably suspected of having a diagnosis of PAD– Subject does not have a suitable finger to attach the FlowMet-R probe– Subject does not have a suitable 1st or 2nd digit to attach the FlowMet-R probe– Subject has undergone revascularization within the last 90 days
Study Procedures and Assessments	
Primary Cohort: 160 control limbs (Healthy Cohort) will be measured according to Event Schedule C, 240 limbs with PAD, including a minimum subset of 54 limbs with claudication and 100 limbs with CLI, will be measured according to Event Schedule A. PAD patients will be measured at three and six month follow-up (as measured from the baseline visit), according to Event Schedule A.
 
Registry: Will be active according to Event Schedule B until data from at least 25 interventional procedures is reached.

3. Introduction

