9.5 Baseline Visit

9.5.1 Relevant Medical History and Demographics

The clinician will document demographics and medical history on the associated Case Report Forms and enter them into the Electronic Data Capture (EDC) system.

For patients that are seen for a vascular (re)intervention and are part of the registry portion of the study, standard information about the patient's scheduled intervention, treatment plan, and follow up schedule will be contained in the record log and uploaded as a digital copy.

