5.2 Rationale

The study will assess the FlowMet-R's ability to provide a simple and continuous method of assessing PAD severity. To achieve the objectives defined in Section 4.1, FlowMet-R measurements will be acquired from the limbs of enrolled patients and the relationship between the FlowMet-R data and positive diagnosis of PAD and CLI will be evaluated at multiple time points (initial measurement, 3 month follow up, and 6 month follow up). Resulting sensitivity, specificity, accuracy, and ROC curves will be generated to demonstrate diagnostic capability. Changes in FlowMet-R data for enrolled patients at each study time point will be compared to corresponding changes in ABI, TBI, or patient symptoms. Finally, the prognostic capability of FlowMet-R data will be assessed by calculating the sensitivity and specificity of predicting whether surgical (re)intervention will be necessary following initial assessment.

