5.6 Exclusion Criteria

Candidates for this study who meet any of the following criteria at the time of the baseline visit are not eligible to be enrolled in this study:

PAD Positive Cohort Exclusion

- Subject is under 40 or unable to consent.
- Subject has any medical condition, which, in the judgment of the Investigator and/or designee, makes the subject a poor candidate for the investigational study.
- Subject is excluded from analysis if no stenosis is found during Doppler but Tibial disease is suspected and Tibial ultrasound is not able to be performed.
- Subject does not have a suitable finger to attach the FlowMet-R probe.
- Subject does not have a suitable 1st or 2nd digit to attach FlowMet-R probe on the limb of interest.
- Subject has undergone revascularization within the last 90 days
- Subject cannot lay safely in a supine position.

Healthy Cohort Exclusion

- Subject is under 40 or unable to consent.
- Subject has any medical condition, which, in the judgment of the Investigator and/or designee, makes the subject a poor candidate for the investigational study.
- One or more limbs has a prior or current diagnosis of PAD, or is reasonably suspected of having a diagnosis of PAD.
- Subject does not have a suitable finger to attach the FlowMet-R probe.
- Subject does not have a suitable 1st or 2nd digit to attach FlowMet-R probe.
- Subject has undergone revascularization within the last 90 days

6. Determination of Sample Size

The rate of PAD and CLI within the population seen at a typical vascular clinic is estimated from a prior investigation. In that study, 100 limbs were assessed using the ABI and graded using the Rutherford classification scheme. PAD (diagnosed via ABI score of <0.9) was present in 63% of limbs. CLI (estimated as having a Rutherford category of ≥ 4) occurred in 15% of limbs. FlowMet-R data was also collected from the above limbs, and the data analysis techniques used in the data analysis section below were applied to build a diagnostic model for PAD and CLI. ROC curves were then generated for the diagnosis of both Claudication and CLI. The resulting area under the curve (AUC) for these ROC curves was 0.67 and 0.80, respectively. However, the Claudicant group AUC had a tighter confidence interval due to larger sample size (84 vs. 22, respectively).

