7.1.3 Analysis Sets

Full Analysis Set

The full analysis set will include all participants and be used for all analyses. Visits outside of visit windows will be assigned to the nearest window. If a participant is missing data for a specific analysis, they will be excluded for that analysis. Within the analysis set, the grouping participants into the healthy, PAD (definitions 1 and 2), and CLI groups are defined in section 4.1.1.1.

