7.10.2 Secondary Objectives

The secondary endpoints will be analyzed as follows:

1. The capability of the acceleration time from the FlowMet-R device to predict a vascular intervention or amputation will occur within three and six months following initial visit will be determined using the AUC from an ROC curve where the endpoint is vascular intervention or amputation within 7 months, which is the end of the 6 month follow-up window. The 95% CI of the AUC will be derived using the method described in DeLong, et al (1998) [15].
2. The capability of the acceleration time from the FlowMet-R device to predict a $\geq 50\%$ stenosis determined using the AUC from an ROC curve where the endpoint is vascular intervention or amputation within 7 months, which is the end of the 6 month follow-up window. The 95% CI of the AUC will be derived using the method described in DeLong, et al (1998) [15].
3. The correlations between the acceleration time from the FlowMet-R device and peripheral artery stenosis, changes in ABI, and changes in TBI will be computed using Pearson correlations. The changes for ABI and TBI will be as follows: 0 to 3 months, 0 to 6 months, and 3 to 6 months.
4. The correlation between the acceleration time from the FlowMet-R device and changes in Rutherford Classification will be computed using the Spearman correlation. The changes for Rutherford Classification will be as follows: 0 to 3 months, 0 to 6 months, and 3 to 6 months.

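### The prognostic ROC does not separate procedures already planned at baseline from newly decided ones, so its AUC does not cleanly answer the stated question

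*Protocol*

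**What the plan says.** **Who enters.** In the protocol Synopsis (Sample Size row), the PAD cohort is open to all comers sent for vascular assessment, and the text adds: "This will include patients in the registry who have a planned endovascular or surgical intervention to address their PAD". The same row describes the registry as holding "Patients diagnosed with PAD at baseline procedure who are scheduled to undergo an endovascular treatment of the lower limbs". The only exclusion that concerns revascularization looks backwards: "Subject has undergone revascularization within the last 90 days" (SAP 5.6, also protocol 8.4). Nothing excludes a procedure that lies ahead.

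**What counts as an event.** SAP 7.10.2 item 1 uses the AUC of acceleration time, where "the endpoint is vascular intervention or amputation within 7 months, which is the end of the 6 month follow-up window". It does not distinguish planned from new procedures.

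**Who is analysed.** SAP 7.1.3: "The full analysis set will include all participants and be used for all analyses". SAP 7.12, which lists changes to the planned analysis, does not mention planned procedures.

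**The aim.** SAP 5.2 (and protocol 5.2) describes the prognostic question as "predicting whether surgical (re)intervention will be necessary following initial assessment".

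**What is recorded.** For registry patients, protocol 9.5.1 says that information on the "scheduled intervention, treatment plan, and follow up schedule will be contained in the record log". The case report form is not among the documents and the event schedules are missing figures, so it cannot be judged whether planned status is already captured for every limb.

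**The concern.** A prognostic AUC should show whether the baseline reading separates limbs that will later need a procedure from limbs that will not. Where the procedure was already decided when the reading was taken, nothing was left to predict, yet the limb is scored as an event. Planned procedures are likely to reflect severity that was already known, and acceleration time is meant to track severity. The AUC may then partly describe how well the device recognises limbs that clinicians had already chosen to treat.

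This is the first-listed secondary objective and the only analysis in the SAP that supports a statement about prognosis. If planned and new procedures are reported as one number, a reader cannot tell which of the two the device relates to.

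**Working it through.** The documents state no event rate, AUC or sample size for the prognostic ROC, so there is no figure of the plan's own to reproduce. The check is what the pooled AUC measures.

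**Step 1: the identity.** Let *w* be the share of events that were planned at baseline, *A_p* the AUC of planned events against non-events, and *A_n* the AUC of new events against the same non-events. The AUC is the chance that a randomly drawn event limb ranks above a randomly drawn non-event limb, and the drawn event is a planned one with probability *w*. Hence

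pooled AUC = *w* × *A_p* + (1 − *w*) × *A_n*.

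This is exact, because the comparison group is the same in both terms.

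**Step 2: inputs.** None of *w*, *A_p* or *A_n* is in the documents. The registry target of at least 25 procedures (Synopsis, Study Procedures and Assessments) is a floor and is not split into planned and new, so it does not give *w*. For illustration, *A_p* is set to 0.67 and 0.80. These are the diagnostic AUCs from the prior study in SAP 6, borrowed only as plausible values. *A_n* is set to 0.50, meaning no prognostic value.

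| Planned share *w* | *A_p* = 0.67 | *A_p* = 0.80 |
|---|---|---|
| 0.25 | 0.25 × 0.67 + 0.75 × 0.50 = 0.5425 | 0.25 × 0.80 + 0.75 × 0.50 = 0.575 |
| 0.50 | 0.50 × 0.67 + 0.50 × 0.50 = 0.585 | 0.50 × 0.80 + 0.50 × 0.50 = 0.65 |
| 0.75 | 0.75 × 0.67 + 0.25 × 0.50 = 0.6275 | 0.75 × 0.80 + 0.25 × 0.50 = 0.725 |

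**Step 3: what the interval could show.** Take 240 PAD limbs, 50 events (25 of them planned) and 190 non-events. The Hanley-McNeil standard error stands in for the SAP's DeLong method, with limbs treated as independent. At a pooled AUC of 0.65 the standard error is 0.0459, and the lower 95% limit is 0.65 − 1.96 × 0.0459 = 0.560. At 0.585 it is 0.0466, and the limit is 0.585 − 1.96 × 0.0466 = 0.494. An interval above 0.5 is thus possible with no ability to predict new procedures, but it does not always follow.

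**Step 4: a less extreme assumption.** Setting *A_n* to 0.50 assumes that new procedures are unrelated to severity, which is the worst case. A simulation relaxed this: 240 limbs, 10 to 40% planned, 5 to 20% of the rest with a new procedure, correlation of 0.3 to 0.5 between acceleration time and severity, logistic severity slope 1 to 2, 300 replicates per setting. With new procedures unrelated to severity, the pooled AUC averaged about 0.53 to 0.66 against about 0.50 for new events. With new procedures following severity at the same slope as planned ones, the pooled AUC exceeded the new-event AUC by only about 0.00 to 0.05. All of these settings are assumptions.

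**Step 5: direction.** The identity works both ways. If *A_p* were 0.50 and *A_n* 0.67, half planned events would give 0.50 × 0.50 + 0.50 × 0.67 = 0.585, which understates the prognostic value of 0.67.

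**The case against.** Four points can be made for the plan as written.

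- **The consequence is limited.** SAP 7.2 says that the objectives are not driven by hypotheses and are reported descriptively. The rule that the interval must exclude 0.5 belongs to the primary objectives (SAP 7.10.1); item 1 of 7.10.2 sets no threshold. Protocol 6.2 also says that FlowMet-R data will not alter treatment, so the reading does not cause the outcome. This stands: the issue is how to interpret a descriptive secondary AUC.
- **Timing is only partly clear.** A reader might infer that every registry procedure was decided before the reading. The documents do not support that. The registry sentence may cover procedures scheduled at or after the baseline visit, and protocol 5 lets registry data collection happen at any time from the initial visit to the final one. Only the cohort sentence about planned interventions shows that some had been planned by enrolment. This narrows the point but does not remove it.
- **The registry has no endpoints.** Protocol 5 says so, but about the data collected in the registry. These patients belong to the PAD cohort, and their procedures still meet the SAP event definition. The blinding described there covers the procedure itself and does not bear on an earlier decision.
- **The objective can be read broadly.** Protocol 4.1.2 speaks of requiring an intervention or amputation within three and six months, which could take in any procedure. That supports keeping the all-procedure ROC in the report. It does not support reporting it alone, given the aim in SAP 5.2.

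**Conclusion.** The concern holds as a mismatch between endpoint and aim. Patients with a planned intervention are enrolled, any procedure within 7 months is an event, all participants are analysed, and no rule in either document separates planned from new procedures. The resulting AUC mixes two questions.

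A reader might go further and infer that the AUC will be inflated, or that the device will appear prognostic when it is not. The documents do not support that. They give neither the planned share nor an AUC for either type of event. The illustrative 0.585 to 0.65 against 0.50 depends on the chosen share, on borrowed AUCs and on new procedures being unrelated to severity. Where new procedures also follow severity, the gap may be about 0.00 to 0.05, and the direction can reverse. Size and direction are unknown.

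The primary objectives are not affected. The change should be made before the secondary analysis is run, because without it the prognostic result cannot be interpreted.

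**What to change.** 1. For each limb, classify whether an intervention or amputation was already scheduled at the time of the baseline FlowMet-R reading, using source records or a yes/no baseline item. The registry record log is not enough: it covers only registry patients and cannot be relied on for planned procedures that were not carried out or that took place outside the registry.
2. In SAP 7.10.2 item 1, base the prognostic statement on the ROC in limbs with nothing scheduled at baseline. This also removes from the non-events any limb whose scheduled procedure was not done within 7 months.
3. Report the all-procedure ROC beside it, with the number of planned and of new events.

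The cost is SAP wording and at most one data item. There are four downsides: fewer events; a wider interval; a narrower severity spectrum, which may itself lower the AUC and should be stated with the result; and retrospective classification for limbs already enrolled, which should be done without sight of the acceleration time. No change to clinical management is involved.

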4.1.2.1 Secondary Endpoints

- Utilize FlowMet-R data to create a predictive model for the prognosis of vascular intervention within a three and six month timeframe from initial visit.
- Employ the predictive model of PAD severity to generate an ROC curve for diagnosis of significant stenosis (>50%) in the iliac, femoral, popliteal, peroneal, or tibial arteries.
- Conduct a correlation test between the predictive model of PAD severity and greatest percent stenosis in the iliac, femoral, popliteal, peroneal, or tibial arteries.

- Conduct a correlation test between changes in the predictive model of PAD severity and corresponding changes in ABI, TBI, and Rutherford Classification between any two study time points.

5. Study Design

This is a non-randomized, multi-center, longitudinal study of healthy subjects and subjects with PAD who are scheduled for ABI, TBI, and either Duplex ultrasound or Angiographic assessments in a vascular clinic. As detailed in the Event Schedules (Section 9.1), subjects will first be evaluated for study inclusion/exclusion. If the subject meets the inclusion criteria and wishes to enroll in the study, they will be asked to sign an informed consent form (ICF) and considered for enrollment. If the subject meets inclusion criteria and is enrolled, the subject will undergo approximately 3 minutes of FlowMet-R blood flow measurements in addition to their routine standard of care examination.

Subjects enrolled in the PAD cohort will be assessed according to Event Schedule A at approximately 0, 3 months, and 6 months. Subject follow ups must meet the scheduled time window within +/- 30 days. Subjects that require a vascular (re)intervention for PAD-related treatment before the final measurement (6 month follow up) will have pertinent data collected and saved in the study registry. The vascular procedure may change the timing with respect to the amount of months after baseline that the follow up visits occur. In that case, the standard of care follow up visits post intervention will be adhered to, and data will be collected from the follow up visits that correspond most closely to timepoints at 3 and/or 6 months post baseline visit.

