8.4 Exclusion Criteria

Candidates for this study who meet any of the following criteria at the time of the baseline visit are NOT eligible to be enrolled in this study:

PAD Positive Cohort Exclusion

- Subject is under 40 or unable to consent.
- Subject has any medical condition, which, in the judgment of the Investigator and/or designee, makes the subject a poor candidate for the investigational study.
- Subject is excluded from analysis if no stenosis is found during Doppler but Tibial disease is suspected and Tibial ultrasound is not able to be performed.
- Subject does not have a suitable finger to attach the FlowMet-R probe.
- Subject does not have a suitable 1st or 2nd digit to attach FlowMet-R probe on the limb of interest.
- Subject has undergone revascularization within the last 90 days

- Subject cannot lay safely in a supine position.

Healthy Cohort Exclusion

- Subject is under 40 or unable to consent.
- Subject has any medical condition, which, in the judgment of the Investigator and/or designee, makes the subject a poor candidate for the investigational study.
- One or more limbs has a prior or current diagnosis of PAD, or is reasonably suspected of having a diagnosis of PAD.
- Subject does not have a suitable finger to attach the FlowMet-R probe.
- Subject does not have a suitable 1st or 2nd digit to attach FlowMet-R probe.
- Subject has undergone revascularization within the last 90 days

9. Study Procedures

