9.7.4 Duplex ultrasound

Color duplex ultrasound measurements shall be used to determine stenosis percentage and location, either during the visit itself or within 30 days prior of the patient visit. Duplex shall be acquired from all limbs enrolled in the study with PAD/CLI as defined via the definitions in Section 8.4. If duplex ultrasound is not available, X-ray angiography will be considered a suitable alternative for calculation of stenosis and location. Color duplex ultrasound imaging will be performed in a similar fashion as the study by Lewis, et al. [30]. First, the distal common femoral artery (CFA) will be imaged and the Doppler waveform (DW) assessed visually for any loss of triphasic flow due to significant iliac disease. If the DW shows indications of this, then the iliac arteries will be assessed for the presence of atherosclerotic disease. The scan will continue distally from the CFA assessing the superficial femoral artery (SFA), popliteal, anterior tibial, posterior tibial, and peroneal arteries in the longitudinal plane. The extent and severity of any arterial disease are assessed by measuring the peak systolic velocity (PSV) from the DW just proximal to and distal through the stenosis. For each measured artery, if perceptible stenosis exists, the location of maximum stenosis will be identified and PSV values distal and proximal to the arterial stenosis will be noted on the CRF. The shape of the waveform (i.e. monophasic, biphasic, or triphasic) measured distal to the stenosis shall also be noted. If no stenosis is noted, this will be indicated on the CRF.

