12.1.3 Analysis of Stenosis

For each artery measured using duplex ultrasound or arterial angiography, the ratio of the PSV distal to the most prominent stenosis to the PCV proximal to the stenosis will be computed (if applicable). The percent stenosis in such arteries will be computed two ways: (1) Percent stenosis = $PSV_{distal}/PSV_{proximal}$, or (2) using the diameter reduction value from Table 3, reprinted from [35].

	Diameter reduction	Waveform	Special broadcasting	PSV distal/PSV proximal
Normal	0	Triphasic	Absent	+++ No change
Mild	1%–19%	Triphasic	Present	<2:1
Moderate	20%–49%	Biphasic	Present	<2:1
Severe	50%–99%	Monophasic	Present	>2:1*

PSV, Peak systolic velocity.

* > 4:1 suggests >75% stenosis, >7:1 suggests > 90% stenosis.

Table 3: Criteria for determining arterial stenosis using peak systolic velocity (PSV) measurements.

Classification of the percent stenosis or presence of greater than 50% stenosis for each limb (used to generate corresponding ROC curve or correlation coefficient) may be determined by either considering a single artery of interest or by considering the artery in each limb with the greatest percent stenosis.

13. Ethics

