4.1.2.1 Secondary Endpoints

- Utilize FlowMet-R data to create a predictive model for the prognosis of vascular intervention within a three and six month timeframe from initial visit.
- Employ the predictive model of PAD severity to generate an ROC curve for diagnosis of significant stenosis (>50%) in the iliac, femoral, popliteal, peroneal, or tibial arteries.
- Conduct a correlation test between the predictive model of PAD severity and greatest percent stenosis in the iliac, femoral, popliteal, peroneal, or tibial arteries.
- Conduct a correlation test between changes in the predictive model of PAD severity and corresponding changes in ABI, TBI, and Rutherford Classification between any two study time points.

5. Investigation Plan

This study is a non-randomized, multi-center, longitudinal study of healthy subjects and subjects with PAD who are scheduled for ABI, TBI, and either Duplex ultrasound or Angiographic assessments in a vascular clinic. Subjects will first be evaluated for study inclusion/exclusion. If the subject meets the inclusion criteria and wishes to enroll in the study, they will be asked to sign an informed consent form (ICF) and considered for enrollment. If the subject meets inclusion criteria and is enrolled, the subject will undergo approximately 3 minutes of FlowMet-R blood flow measurements in addition to their routine standard of care examination.

Subjects enrolled in the PAD cohort will be assessed according to Event Schedule A in the clinical investigation protocol (CIP) at approximately 0, 3 months, and 6 months. Subject follow ups must meet the scheduled time window within +/- 30 days. Subjects that require a vascular (re)intervention for PAD-related treatment before the final measurement (6 month follow up) will have pertinent data collected and saved in the study registry. The vascular procedure may change the timing with respect to the amount of months after baseline that the follow up visits occur. In that case, the standard of care follow up visits post intervention will be adhered to, and data will be collected from the follow up visits that correspond most closely to timepoints at 3 and/or 6 months post baseline visit.

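### The exclusion for suspected but un-imaged tibial disease applies only when no stenosis at all is found, while the endpoint is >50% stenosis, so some limbs stay in as unverified negatives

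*Protocol*

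**What the plan says.** The Protocol synopsis removes a PAD-cohort subject under three joint conditions. One is that a tibial scan could not be done; the other two are in the words "Subject is excluded from analysis if no stenosis is found during Dopper Ultrasound, but Tibial disease is suspected". Protocol 8.4 has the same trigger, "Subject is excluded from analysis if no stenosis is found during Doppler but Tibial disease is suspected", and SAP 5.6 repeats it unchanged.

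The endpoint that this rule bears on is in Protocol 4.1.2.1: "generate an ROC curve for diagnosis of significant stenosis (>50%) in the iliac, femoral, popliteal, peroneal, or tibial arteries". SAP 4.1.2.1 has the same threshold and arteries: "significant stenosis (>50%) in the iliac, femoral, popliteal, peroneal, or tibial arteries". A second endpoint is a correlation with "greatest percent stenosis in the iliac, femoral, popliteal, peroneal, or tibial arteries".

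On what counts as a finding, Protocol 9.7.4 says that for each measured artery, "if perceptible stenosis exists, the location of maximum stenosis will be identified"; the absence of stenosis is a separate CRF entry. The criteria table in Protocol 12.1.3 has two visible grades below the threshold, mild (1–19%) and moderate (20–49%), both distinct from normal (0). The same section computes stenosis for the arteries that were measured. It classifies the limb on one artery of interest or "by considering the artery in each limb with the greatest percent stenosis".

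Healthy subjects get no imaging beyond standard of care. Those with normal ABI and TBI are assumed to have no significant stenosis (Protocol section 5, SAP section 5).

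**The concern.** The rule accepts that a negative stenosis label is unsafe when suspected tibial disease could not be seen. That reasoning does not depend on whether the arteries that were seen are perfectly clear or have a minor lesion. With a threshold of 50%, a visible 30% femoral lesion says no more about the tibial arteries than a visible 0%. Yet the first limb is kept and the second removed.

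A kept limb of this kind joins the stenosis-negative class without verification. If its unseen tibial or peroneal lesion does exceed 50%, the stenosis ROC has a diseased limb among its negatives, and the correlation has a greatest percent stenosis that is too low. If such limbs read more like diseased than undiseased ones, both results move toward no association.

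Three further details do not fit the endpoint. The rule names Doppler only, although angiography is an accepted alternative (Protocol 9.7.4, 9.7.5). It names tibial arteries only, although the endpoint includes the peroneal. It acts on the subject, although Protocol 12.1.3 classifies the limb.

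**Working it through.** **Step 1: rule against endpoint.** Take a PAD-cohort limb with suspected tibial disease and no tibial imaging, classified on its worst measured artery.

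| Worst visible lesion | Rule as written | Label in the stenosis ROC | Is the label safe? |
|---|---|---|---|
| 0% | excluded | none | not applicable |
| above 0, not over 50% | kept | negative | no, the tibials are unknown |
| over 50% | kept | positive | yes, whatever the tibials show |

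The unprotected band is the middle row, essentially the mild and moderate grades in Protocol 12.1.3.

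**Step 2: illustration of size.** The plan states no sample size, AUC or rate for the stenosis endpoint, so there is no figure to reproduce. Let m be the share of labelled negatives that truly exceed 50%, and assume that they read like the labelled positives. A positive compared with such a limb is a coin toss, so

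AUC observed = (1 − m) × AUC true + m × 0.5, and the loss is m × (AUC true − 0.5).

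Assumed inputs: true AUC 0.75, 8 limbs in the unprotected band, 40 labelled negatives in the PAD cohort. Taken from the plan: 160 control limbs (Protocol 8.1, SAP 5.3).

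- Healthy limbs counted as negatives: m = 8/(160 + 40) = 4%. AUC = 0.96 × 0.75 + 0.04 × 0.5 = 0.74, a loss of 0.01.
- PAD-cohort limbs only: m = 8/40 = 20%. AUC = 0.80 × 0.75 + 0.20 × 0.5 = 0.70, a loss of 0.05.

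Both lines take all 8 as truly over 50%. If only 4 are, m is 4/200 = 2% or 4/40 = 10%, and the losses halve to 0.005 and 0.025.

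**Step 3: other true AUCs.** The pilot AUCs in Protocol 12.1.1, 0.67 and 0.80, are for claudication and CLI, so they only mark a plausible range.

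| True AUC | m = 4% | m = 20% |
|---|---|---|
| 0.67 | 0.663 | 0.636 |
| 0.75 | 0.740 | 0.700 |
| 0.80 | 0.788 | 0.740 |

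The same true AUC is used with and without healthy limbs for simplicity. In practice it would probably differ between the two comparisons.

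**The case against.** **The affected group is narrow.** Protocol 9.7.4 calls for anterior tibial, posterior tibial and peroneal scanning, and angiography can fill gaps. A limb is affected only if four things coincide: a sub-threshold visible lesion, suspected tibial disease, a failed tibial scan and no angiogram. This stands, and the count is unknown.

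**The negative class may be large.** With healthy limbs assumed free of significant stenosis, and a full analysis set used throughout (SAP 7.1.3), the loss in the example is 0.01. This stands too. A reader might infer a loss of 0.05 or more as the general result. The documents do not support that, since it needs a PAD-only ROC and an assumed 40 negatives. They also do not say outright which comparison is meant.

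**The complete-case rule might remove these limbs.** SAP 7.1.3 and 7.4 drop cases with missing data for an analysis. Read strictly, this could cover a limb with unseen tibials. The reading is weak. Protocol 9.7.4 scans the iliac arteries only after an abnormal femoral waveform, so limbs are meant to be classified on incomplete imaging. A strict reading would also make the exclusion bullet redundant.

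**The wording might mean no significant stenosis.** The plan states the 50% threshold where it wants it, and Protocol 9.7.4 treats any perceptible lesion as a finding.

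**The label might not be false.** A reader might call these limbs false negatives. Their status is unknown, and nothing in the documents shows that their unseen lesions exceed 50%. Protocol 12.1.3 also allows classification on a single artery of interest, so the negative label follows from the worst-artery reading and is not the only possible outcome.

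**Conclusion.** The mismatch holds in all three copies of the rule, and no other text clearly closes it. A limb with a visible lesion above 0 but not over 50%, and with suspected, un-imaged tibial disease, is kept as an unverified negative. It may also enter the correlation too low.

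The probable direction is toward no association. The size cannot be known from the documents. For 8 such limbs, all truly over 50%, it is about 0.01 in AUC with the healthy limbs as negatives and about 0.05 in a PAD-only ROC with an assumed 40 negatives. Both figures rest on an assumed true AUC of 0.75 and on mislabelled limbs reading like positives.

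A reader might also infer that the primary results are mislabelled. They are not: the PAD and CLI definitions (Protocol and SAP 4.1.1.1.1) use ABI, TBI, postexercise testing and symptoms, not stenosis. The two affected analyses are secondary, and SAP 7.2 presents results descriptively. The case for acting is that the correction is cheap and follows the plan's own logic.

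**What to change.** Add a limb-level rule to Protocol 12.1.3 and SAP 7.10.2, with cross-references from the synopsis, Protocol 8.4 and SAP 5.6:

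- **Indeterminate:** no stenosis >50% is found in the imaged arteries by duplex or angiography, tibial or peroneal disease is suspected, and those arteries could not be assessed by either method. Leave such limbs out of the stenosis ROC and the stenosis correlation.
- **Positive:** any imaged listed artery is >50%, even if the tibial arteries were not seen.
- **Healthy cohort:** limbs with normal ABI and TBI stay negative, as the plan already assumes. Requiring full imaging for every negative would remove these un-imaged controls, up to 160 limbs, and also PAD limbs with no suspicion of tibial disease.
- **Scope:** the rule governs the stenosis analyses only, so that the wider trigger does not take more subjects out of the primary PAD and CLI analyses. State separately whether the existing subject-level bullet still applies to those.
- **Threshold:** use one throughout. SAP 7.10.2 item 2 has ≥50%, the endpoint has >50%. The same item names intervention or amputation as the ROC outcome. That is a separate defect, but it must be settled for this rule to operate.
- **Reporting:** give the number of indeterminate limbs, and say whether healthy limbs are in the ROC.

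Cost: wording in two documents and probably a few limbs lost from two secondary analyses. No new imaging is needed. One limitation remains: a limb with a visible lesion >50% and unseen tibials enters the correlation at a value that is only a lower bound, so these limbs should be counted as well.
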